5.6.1. Deviations Assessed Prior to Dosing

At Screening, the investigator will assess subjects against the inclusion and exclusion criteria as set out in Sections 4.1 and 4.2 of the protocol.

5.6.2. Deviations Assessed Post-Dosing

A full list of protocol deviations for the study report will be compiled prior to database closure. Any significant deviation from the protocol will be reviewed prior to database closure and a decision taken regarding evaluation for each analysis population.

6. ENDPOINTS AND COVARIATES

6.1. Efficacy Endpoint(s)

None.

6.2. Safety Endpoints

Any events occurring following PF-05221304 dosing or increasing in severity will be counted as treatment emergent.

Events that occur in a non-treatment period (for example Follow-up) will be counted as treatment emergent and attributed to the dose taken.

The following data are considered in standard safety summaries (see protocol for collection days and list of parameters):

- *adverse events,*
- *laboratory data,*
- *vital signs data,*
- *ECG results.*

6.3. Other Endpoints

6.3.1. PK Endpoints

Blood samples for PK analysis of PF-05221304 will be taken according to the Schedule of Activities given in the protocol.

The following PK parameters will be calculated for PF-05221304 (if possible) from the concentration-time data using standard non-compartmental methods:

Table 3. Noncompartmental PK Parameters

PK Parameter	Analysis Scale	PF-05221304	Definition
AUC_{last}	ln	A, D	Area under the plasma concentration-time profile from time zero to the time of the last quantifiable concentration (C_{last})
$AUC_{last,u}$	ln	A, D	Unbound area under the plasma concentration-time profile from time zero to the time of the last quantifiable concentration (C_{last})
AUC_{inf}^*	ln	A, D	Area under the plasma concentration-time profile from time zero extrapolated to infinite time
$AUC_{inf,u}^*$	ln	A, D	Unbound area under the plasma concentration-time profile from time zero extrapolated to infinite time
C_{max}	ln	A, D	Maximum plasma concentration
$C_{max,u}$	ln	A, D	Unbound maximum plasma concentration
T_{max}	R	D	Time for C_{max}
$t_{1/2}^*$	R	D	Terminal half-life
CL/F^*	ln	A, D	Apparent clearance
CL_u/F^*	ln	A, D	Unbound apparent clearance
V_z/F^*	ln	A, D	Apparent volume of distribution
V_{z_u}/F^*	ln	A, D	Unbound apparent volume of distribution
Fu^+	R	D	Fraction unbound

Key: A=analyzed using statistical model, D=displayed with descriptive statistics,
ln=natural-log transformed, R=raw (untransformed), *=if data permits; u=unbound fraction
+ = Reported in eNCA as protein free fraction.

6.3.2. Other Endpoints

None.

6.4. Covariates

No covariate for primary analysis (ie ANOVA) will be included in the model. For secondary analysis (ie ANCOVA), age, and body weight will be included in the model. Additionally, gender may also be included as a covariate if approximately 50% of each cohort is female.

7. HANDLING OF MISSING VALUES

For the analysis of safety endpoints, the sponsor data standard rules for imputation will be applied.

7.1. Concentrations Below the Limit of Quantification

In all data presentations (except listings), PK concentrations below the limit of quantification (BLQ) will be set to zero. (In listings BLQ values will be reported as “<LLQ”, where LLQ will be replaced with the value for the lower limit of quantification.)

In all data presentations (except listings), CP-I and CP-III concentrations below the limit of quantification (BLQ) will be set to LLQ/2. (In listings BLQ values will be reported as “<LLQ”, where LLQ will be replaced with the value for the lower limit of quantification.)

7.2. Deviations, Missing Concentrations and Anomalous Values

In summary tables and plots of median profiles, statistics will be calculated having set concentrations to missing if 1 of the following cases is true:

1. A concentration has been collected as ND (ie not done) or NS (ie no sample),
2. A deviation in sampling time is of sufficient concern or a concentration has been flagged anomalous by the pharmacokineticist.

Note that summary statistics will not be presented at a particular time point if more than 50% of the data are missing.

7.3. Pharmacokinetic Parameters

Actual PK sampling times will be used in the derivation of PK parameters.

If a PK parameter cannot be derived from a subject’s concentration data, the parameter will be coded as NC (ie not calculated). (Note that NC values will not be generated beyond the day that a subject discontinues.)

In summary tables, statistics will be calculated by setting NC values to missing; and statistics will be presented for a particular hepatic function cohort with ≥ 3 evaluable measurements. For statistical analyses (ie analysis of variance), PK parameters coded as NC will also be set to missing; and statistical analyses will not be performed for a particular parameter if more than 50% of the data are NC.

If an individual subject has a known biased estimate of a PK parameter (due for example to an unexpected event such as vomiting before all the compound is adequately absorbed in the body), this will be footnoted in summary tables and will not be included in the calculation of summary statistics or statistical analyses.

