7.1.2. Plasma for Determination of PF-05221304 Unbound Fraction

During the study, a blood sample (12 mL) to provide sufficient plasma for unbound fraction determination will be collected into an appropriately labeled tube containing K₂EDTA as defined in the Schedule of Activities [Table A](#).

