2.1. Study Design

This is a non-randomized, open-label, single-dose, parallel-cohort, multisite study to investigate the effect of varying degrees of hepatic impairment on the plasma pharmacokinetics (total and unbound) of PF-05221304 after a single oral 25 mg dose administered in the fed state. A total of approximately 24 subjects with varying degrees of hepatic function will be enrolled into the study to ensure that up to 6 evaluable subjects in each of the 4 hepatic function cohorts complete the study. Subjects will be selected based on their Child-Pugh score as shown in Table 1.

Table 1. Hepatic Function Categories Based on Child Pugh Score

Cohort	Description	Child-Pugh Score	Number of Subjects
1	Without hepatic impairment	Not Applicable	6 ^a
2	Mild hepatic impairment	Class A (5 to 6 points)	6
3	Moderate hepatic impairment	Class B (7 to 9 points)	6
4	Severe hepatic impairment	Class C (10 to 15 points)	6 ^b

- a. Additional subjects may be dosed to a maximum of 10 subjects to ensure mean age is ± 5 years and mean body weight ± 10 kg of this cohort is in line with pooled average assessed when $\geq 75\%$ of subjects are dosed across other 3 cohorts
- b. If recruitment across the sites selected proves to be prohibitive, study will dose only 4 subjects in this cohort

Child-Pugh scores will be determined as described in Table 2, at the screening visit. Recruitment for subjects meeting the criteria for Cohorts 3 and 4 will initiate first. Recruitment for subjects in Cohort 2 will start when approximately 50% of total subjects across Cohorts 3 and 4 (ie, 6 of 12) have been dosed. Subjects in Cohort 1 will be recruited last to match the average demographics (at a minimum, age and weight; and as much as practically possible gender) across the pooled Cohorts 2 through 4.

Table 2 Child-Pugh Classification (CPC) of Liver Dysfunction

Table 2-1: Scoring for Child-Pugh Classification

Cohort	CPC	Level of dysfunction	Total Score (tally based on assessment of parameters in Table 2-2)
1	Not Applicable	Without hepatic impairment	Not Applicable
2	A	Mild	5-6
3	B	Moderate	7-9
4	C	Severe	≥ 10

Table 2-2: Derivation of Child-Pugh Classification Score

Assessment Parameters	Assigned score for observed findings		
	1 point	2 point	3 point
Encephalopathy grade (refer to Table 2-3 below)	0	1 or 2	3 or 4 ^a (or Requiring intervention ^b)
Ascites	Absent	Asymptomatic	Requiring intervention
Serum total bilirubin, mg/dL	< 2	2 to 3	> 3
Serum albumin, g/dL	> 3.5	2.8 to 3.5	< 2.8

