8.2. Statistical Analyses of PK Parameters

One-way analysis of variance (ANOVA) will be used to compare the natural log transformed PF-05221304 AUC_{inf} , AUC_{last} and C_{max} , unbound AUC_{inf} ($AUC_{inf,u}$), unbound AUC_{last} ($AUC_{last,u}$), and unbound C_{max} ($C_{max,u}$), as data permit, for each of the hepatic impairment classification cohorts (Test) to the cohort without hepatic impairment (Reference). Estimates of the adjusted mean and corresponding 90% confidence intervals will be obtained from the model for each cohort. Estimates of the adjusted mean differences (Test-Reference) and corresponding 90% confidence intervals will be obtained from the model as well. The adjusted mean estimates and adjusted mean differences and 90% confidence intervals for the estimates and differences will be exponentiated to provide estimates of adjusted geometric means and estimates of the ratio of adjusted geometric means (Test/Reference) and 90% confidence intervals for the estimates and for the ratios respectively (see Appendix 1 for SAS code).

Additionally, as an exploratory analysis, age, body weight, and gender (see Section 6.4) will be explored as a covariate/factor in the ANOVA/ANCOVA model, as appropriate (see Appendix 1 for SAS code).

Linear regression may be used to analyze the potential relationship between the following PK parameters -AUC_{inf}, and CL/F separately - and the following hepatic function - serum albumin, prothrombin time, and total bilirubin separately -. Estimates of the slope and intercept, together with their precision (90% confidence interval [CI]), and the coefficient of determination (ie R-squared and adj-R-squared) will be obtained from the model.

Plots of PK parameters -AUC_{inf}, and CL/F separately - versus hepatic function - serum albumin, prothrombin time, total bilirubin separately - will be constructed. A regression line and 90% confidence region for the PK parameters and hepatic function will be included. (See appendix 1 for example of SAS code to produce the figure).

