Residuals from the models will be examined for normality and the presence of outliers via visual inspection of plots of residuals vs predicted values and normal probability plots of residuals but these will not be included in the clinical study report. If there are major deviations from normality or outliers then the effect of these on the conclusions will be investigated through alternative transformations and/or analyses excluding outliers. Alternative model structure may also be considered. Justification for any alternative to the planned analysis will be given in the report of the study.

The following PK parameters will be summarized by hepatic function Cohort:

Table 4. PK Parameters to be Summarized Descriptively by Cohort	
Parameter	Summary Statistics
C _{max} , AUC _{last} , AUC _{inf} , CL/F, V _z /F, AUC _{inf,u} , AUC _{last,u} , C _{max,u} , CL _u /F, and V _{zu} /F	N, arithmetic mean, median, cv%, standard deviation, minimum, maximum, geometric mean and geometric cv%.
T _{max}	N, median, minimum, maximum.
t _{1/2, fu}	N, arithmetic mean, median, cv%, standard deviation, minimum, maximum.

Box and whisker plots for PF-05221304 AUC_{inf}, AUC_{last}, C_{max}, AUC_{inf,u}, AUC_{last,u}, and C_{max,u} individual subject parameters will be plotted by hepatic function cohort and overlaid with geometric means.

Supporting data from the estimation of t^{1/2} and AUC_{inf} will be listed by cohort: terminal phase rate constant (k_{e1}); goodness of fit statistic from the log-linear regression (r²); the percent of AUC_{inf} based on extrapolation (AUC_{extrap}%); and the first, last, and number of time points used in the estimation of k_{e1}. This data may be included in the clinical study report.

Presentations for PF-05221304 concentrations will include:

- a listing of all concentrations sorted by hepatic function cohort (present in heading), subject id and nominal time postdose. The concentration listing will also include the actual times. Deviations from the nominal time will be given in a separate listing.
- a summary of concentrations by hepatic function cohort and nominal time postdose, where the set of statistics will include n, mean, median, standard deviation, coefficient of variation (cv), minimum, maximum and the number of concentrations above the lower limit of quantification.

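### Does the unstated denominator of the SAP's 50% not-calculated rule leave the primary exposure ratios open to choice?

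*SAP*

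**What the plan says.** SAP 7.3 contains two rules about parameters that cannot be derived.

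- **Summary tables.** NC values are set to missing, and "statistics will be presented for a particular hepatic function cohort with" at least three evaluable values. The unit is the cohort.
- **ANOVA.** NC values are again set to missing, and "statistical analyses will not be performed for a particular parameter if more than 50% of the data are NC". The unit is the parameter; no denominator is given.

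The same section says that known biased estimates "will not be included in the calculation of summary statistics or statistical analyses", without saying whether they count towards the 50%.

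SAP 8.2 describes the model output: "Estimates of the adjusted mean and corresponding 90% confidence intervals will be obtained from the model for each cohort", followed by the Test/Reference ratios. SAP Table 4 lists the descriptive statistics for the exposure parameters: "N, arithmetic mean, median, cv%, standard deviation, minimum, maximum, geometric mean and geometric cv".

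Cohort sizes may depart from 6. For the severe cohort, if recruitment is prohibitive, "study will dose only 4 subjects in this cohort"; for the reference cohort, "Additional subjects may be dosed to a maximum of 10 subjects". SAP 4.1 and 4.2 plan no hypothesis test and no decision rule.

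**The concern.** The 50% rule decides whether a primary comparison appears in the report. If its denominator is open, one data set could yield three ratios, two, or none. The study is open-label and the sponsor may look at data while it runs (SAP 3), so the reading could in principle be chosen with results in view.

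The two rules also act on the same number. The planned ANOVA has no covariates, so a cohort's adjusted geometric mean is its plain geometric mean. With 4 severe subjects and 2 NC, the model output would print a mean that the summary table withholds. N is in the same withheld list, so a ratio resting on two people might appear with no count.

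Missing parameters need not come only from a poorly defined terminal phase. Protocol 7.1.2 provides one binding sample per subject ("a blood sample (12 mL) to provide sufficient plasma for unbound fraction determination will be collected"), and losing it removes the unbound Cmax and both unbound AUCs for that subject.

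**Working it through.** **Inputs.** Cohorts of 6, severe possibly 4, reference up to 10 (SAP 2.1). Log-scale SDs of 0.16, 0.23 and 0.28 (Protocol Table 4). One-way ANOVA with 90% intervals (SAP Appendix 1). Neither document gives an expected NC rate.

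**1. Reproducing Protocol Table 4.** With half-width h = t(0.95, 10) × SD × √(2/6) × √(χ²(0.80, 10)/10), precision is 1 − exp(−h) and the interval is 2·exp(±h).

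| SD | h | Precision | Interval | Protocol |
|---|---|---|---|---|
| 0.16 | 0.1941 | 17.6% | (1.65; 2.43) | 18% (1.65; 2.43) |
| 0.23 | 0.2790 | 24.3% | (1.51; 2.64) | 24% (1.51; 2.64) |
| 0.28 | 0.3397 | 28.8% | (1.42; 2.81) | 29% (1.42; 2.81) |

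The table is a two-sample calculation (10 df) with an 80% tolerance factor, so its SDs can be used as they stand.

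**2. What each reading gives.** Other cohorts are complete with n = 6. The last column counts values left in the affected cohort.

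| Case | All subjects | Test + Reference pair | Own cohort | Left |
|---|---|---|---|---|
| 3 of 6 severe NC | 3/24 = 12.5% | 3/12 = 25% | 50% | 3 |
| 4 of 6 severe NC | 4/24 = 16.7% | 4/12 = 33.3% | 66.7% | 2 |
| 2 of 4 severe NC | 2/22 = 9.1% | 2/10 = 20% | 50% | 2 |
| 3 of 4 severe NC | 3/22 = 13.6% | 3/10 = 30% | 75% | 1 |
| 6 of 10 reference NC | 6/28 = 21.4% | 6/16 = 37.5% | 60% | 4 |

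Counted over all subjects or per pair, every row gives three ratios. The per-cohort count differs in rows 2, 4 and 5. Getting two ratios in rows 2 and 4 needs a further step that SAP 7.3 does not state: removing one contrast and keeping the rest. What the SAP does state is that the analysis of the parameter is not performed, and Appendix 1 fits one model to all four cohorts.

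**3. When the two rules disagree.** With 2 of 4 severe values NC, 50% is not more than 50%, so the ANOVA runs on every reading while the summary table shows nothing for that cohort. With 0 or 1 of 4 NC there is no disagreement. It also arises, on an all-subject or per-pair count, with 3 of 4 or with 4 or 5 of 6 NC. For assumed independent NC rates of 10%, 20% and 30%:

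- 2 of 4 NC, 6p²(1−p)²: 4.9%, 15.4%, 26.5%;
- 4 or 5 of 6 NC, 15p⁴(1−p)² + 6p⁵(1−p): 0.1%, 1.7%, 7.0%.

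**4. What a thin severe cohort does to the ratio.** Interval = 2·exp(±t(0.95, df) × SD × √(1/6 + 1/n)), with n evaluable severe subjects and df = 18 + n − 4.

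| n | df | SD 0.16 | SD 0.28 |
|---|---|---|---|
| 6 | 20 | (1.71; 2.35) | (1.51; 2.64) |
| 3 | 17 | (1.64; 2.44) | (1.42; 2.82) |
| 2 | 16 | (1.59; 2.51) | (1.34; 2.98) |
| 1 | 15 | (1.48; 2.71) | (1.18; 3.40) |

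The loss of information appears in the width. Simulated coverage with equal SDs (1,000,000 runs per case) was 90.0%, to 0.1 point, at each n.

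**5. Excluded biased values.** Counted over 24 subjects, each adds 1/24 = 4.2 points. The rule first trips at 13/24 = 54.2%, so their treatment matters only near 12 or 13 lost values.

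**The case for a change.** The best argument for a change is that the all-subject reading is natural but not certain. SAP 7.2 suppresses summary statistics at a time point when over half the data are missing, and SAP 8.2 produces those summaries by cohort, so similar wording there points to a per-cohort count. Pooling also makes the rule weak: all six reference values could be NC (6/24 = 25%) and the rule would not trip. The clarification would take two sentences and a count column.

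The silence on the denominator is real, and so is the mismatch between tables. The weakness of the pooled rule does little harm: with no reference values there is no ratio to report, and with few values the interval widens.

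A second argument is that width may not be sufficient warning. If the severe SD were 0.28 and the others 0.16 (an assumption; Protocol Table 4 assigns no SD to a cohort), coverage would be 73.5% with two severe subjects. But it would be 84.4% with six, and in the reverse case 97.2% and 93.0%. This comes from pooling unequal variances, and naming a denominator does not cure it.

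The fraction unbound adds less than it seems. SAP Table 3 makes it descriptive only, so it has no ratio for the rule to remove. The point does apply to the unbound Cmax and AUCs.

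The missing count is also less likely than a literal reading suggests. SAP 8.2 plots individual exposure parameters by cohort, so a cohort reduced to two values would be visible.

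**Conclusion.** This is a gap that analysts fill sensibly, and closing it brings no gain in the results. Read by its own unit, the 50% rule is counted per parameter over all subjects and stops the whole analysis of that parameter or none of it; all three ratios are then reported in every case worked above. The three-value minimum is confined to summary tables, so printing an ANOVA mean from two values breaks no rule. That mismatch is conditional on several severe values being lost and is independent of the denominator.

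At its largest among the two-subject cases shown, the interval around a 2-fold ratio is (1.34; 2.98) instead of (1.51; 2.64). All the intervals shown exclude 1, including those with one subject. Stating the all-subject denominator and printing n would leave each estimate and interval as it is.

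This rests on equal variances across cohorts and on values being lost independently of their size. The 10–30% NC rates are illustrative. Naming the denominator would not repair a failure of either assumption.

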8. STATISTICAL METHODOLOGY AND STATISTICAL ANALYSES

8.1. Statistical Methods

The effect of the hepatic impairment on PK parameters will be assessed by constructing 90% confidence intervals around the estimated difference between each of the Test (impaired cohorts) and the Reference (normal hepatic function cohort) using a one-way ANOVA model based on natural log transformed data.

The relationship between PK parameters and hepatic function will be determined by a linear regression model.

CCI

8.2. Statistical Analyses of PK Parameters

One-way analysis of variance (ANOVA) will be used to compare the natural log transformed PF-05221304 AUC_{inf} , AUC_{last} and C_{max} , unbound AUC_{inf} ($AUC_{inf,u}$), unbound AUC_{last} ($AUC_{last,u}$), and unbound C_{max} ($C_{max,u}$), as data permit, for each of the hepatic impairment classification cohorts (Test) to the cohort without hepatic impairment (Reference). Estimates of the adjusted mean and corresponding 90% confidence intervals will be obtained from the model for each cohort. Estimates of the adjusted mean differences (Test-Reference) and corresponding 90% confidence intervals will be obtained from the model as well. The adjusted mean estimates and adjusted mean differences and 90% confidence intervals for the estimates and differences will be exponentiated to provide estimates of adjusted geometric means and estimates of the ratio of adjusted geometric means (Test/Reference) and 90% confidence intervals for the estimates and for the ratios respectively (see Appendix 1 for SAS code).

Additionally, as an exploratory analysis, age, body weight, and gender (see Section 6.4) will be explored as a covariate/factor in the ANOVA/ANCOVA model, as appropriate (see Appendix 1 for SAS code).

Linear regression may be used to analyze the potential relationship between the following PK parameters -AUC_{inf}, and CL/F separately - and the following hepatic function - serum albumin, prothrombin time, and total bilirubin separately -. Estimates of the slope and intercept, together with their precision (90% confidence interval [CI]), and the coefficient of determination (ie R-squared and adj-R-squared) will be obtained from the model.

Plots of PK parameters -AUC_{inf}, and CL/F separately - versus hepatic function - serum albumin, prothrombin time, total bilirubin separately - will be constructed. A regression line and 90% confidence region for the PK parameters and hepatic function will be included. (See appendix 1 for example of SAS code to produce the figure).

Residuals from the models will be examined for normality and the presence of outliers via visual inspection of plots of residuals vs predicted values and normal probability plots of residuals but these will not be included in the clinical study report. If there are major deviations from normality or outliers then the effect of these on the conclusions will be investigated through alternative transformations and/or analyses excluding outliers. Alternative model structure may also be considered. Justification for any alternative to the planned analysis will be given in the report of the study.

The following PK parameters will be summarized by hepatic function Cohort:

Table 4. PK Parameters to be Summarized Descriptively by Cohort	
Parameter	Summary Statistics
C _{max} , AUC _{last} , AUC _{inf} , CL/F, V _z /F, AUC _{inf,u} , AUC _{last,u} , C _{max,u} , CL _u /F, and V _{zu} /F	N, arithmetic mean, median, cv%, standard deviation, minimum, maximum, geometric mean and geometric cv%.
T _{max}	N, median, minimum, maximum.
t _{1/2, fu}	N, arithmetic mean, median, cv%, standard deviation, minimum, maximum.

Box and whisker plots for PF-05221304 AUC_{inf}, AUC_{last}, C_{max}, AUC_{inf,u}, AUC_{last,u}, and C_{max,u} individual subject parameters will be plotted by hepatic function cohort and overlaid with geometric means.

Supporting data from the estimation of t^{1/2} and AUC_{inf} will be listed by cohort: terminal phase rate constant (k_{e1}); goodness of fit statistic from the log-linear regression (r²); the percent of AUC_{inf} based on extrapolation (AUC_{extrap}%); and the first, last, and number of time points used in the estimation of k_{e1}. This data may be included in the clinical study report.

Presentations for PF-05221304 concentrations will include:

- a listing of all concentrations sorted by hepatic function cohort (present in heading), subject id and nominal time postdose. The concentration listing will also include the actual times. Deviations from the nominal time will be given in a separate listing.
- a summary of concentrations by hepatic function cohort and nominal time postdose, where the set of statistics will include n, mean, median, standard deviation, coefficient of variation (cv), minimum, maximum and the number of concentrations above the lower limit of quantification.
- median concentrations time plots (on both linear and semi-log scales) against nominal time postdose by hepatic function cohort (all hepatic function cohorts on the same plot per scale, based on the summary of concentrations by hepatic function cohort and time postdose).
- mean concentrations time plots (on both linear and semi-log scales) against nominal time postdose by hepatic function cohort (all hepatic function cohorts on the same plot per scale, based on the summary of concentrations by hepatic function cohort and time postdose).
- individual concentration time plots by hepatic function cohort (on both linear and semi-log scales) against actual time postdose (there will be separate spaghetti plots for each hepatic function cohort per scale).

For summary statistics, median and mean plots by sampling time, the nominal PK sampling time will be used. For individual subject plots by time, the actual PK sampling time will be used.

